	 Occurrence of abnormalities (Grade ≥ 3) in laboratory test values, markedly abnormal vital sign measurements, markedly abnormal physical examination measurements, clinically significant abnormal ECG, marked changes in ECOG PS
	 Incidence, severity and outcomes of RT-induced toxicity

Objectives	Endpoints (Outcome Measures)							
Pharmacokinetics								
To characterize the pharmacokinetics of M3814 and avelumab when given in combination with radiotherapy	 Pharmacokinetic profile of avelumab in terms of pharmacokinetic parameter estimates, as feasible (e.g. C_{max}, C_{mln}, Racc[C_{max}], Racc[AUC] and t_{1/2}) 							
	 Pharmacokinetic profile of M3814 in terms of pharmacokinetic parameter estimates (C_{max}, t_{max}, C_{min}, C_{avg}, fluctuation index, AUC_{0-t}, AUC_{0-m}, Racc[C_{max}], Racc[AUC], t_{1/2}, Vz/f, CL/f, and Λz) 							
Immunogenicity								
To evaluate the immunogenicity of avelumab in combination with M3814 plus radiotherapy	Immunogenicity as measured by ADA							
Efficacy								
To evaluate the preliminary antitumor activity of M3814 when given in combination with avelumab and radiotherapy in participants with locally advanced and advanced solid tumors	 Confirmed BOR, DOR assessed from CR or PR until PD, death, or last tumor assessment, and PFS time according to RECIST v 1.1 as assessed by the Investigator 							
	 Tumor size measurement based on Investigator assessment according to RECIST v 1.1 from the first study interventions dose until confirmed PD or start of new cancer treatment 							
	Overall Survival							
ADA=antidrug antibody, BOR=best overall respon	se, CR=complete response, DLT=dose-limiting toxicity							

ADA=antidrug antibody, BOR=best overall response, CR=complete response, DLT=dose-limiting toxicity, DOR=duration of response, ECG=electrocardiogram, ECOG PS=Eastern Cooperative Oncology Group Performance Status, MTD=maximum tolerated dose, NCI-CTCAE=National Cancer Institute-Common Terminology Criteria for Adverse Events, PD=progressive disease, PFS=progression-free survival, PR=partial response, RECIST=Response Evaluation Criteria In Solid Tumors, RP2D=recommended Phase II dose, RT=radiotherapy.

Part FE

Objectives	Endpoints (Outcome Measures)							
Primary								

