Clinical Examination of Tissues in RT Area			х	х		х	x	Required on each day of RT schedule.
ECOG PS	X	X	X	X		Х	X	
Adverse Event Assessment	X	X	X	X	X	X	X	
Concomitant Medication	X	X	X	X	X	X	X	

Study Period	Screeni ng	DLT	DLT Evaluation Period Week 1 to 4 (M3814 + RT + avelumab)				4	Notes
Study Visit	1	2	3-6	7-10	11	12	13	
Study Day (± Visit window)	-35 to -1	1	2-5 (± 1)	8-11 (± 1)	12	15 (± 1)	29 (± 1)	
M3814		X	x	X	X			M3814 QD 5 d/wk (only on days of radiation). See Section 6.6.5.2.
RT 3 Gy × 10 (5 FD/W)		X	x	X	X			RT 3 Gy/fraction, 5 FD/wk. RT to be given 1.5 h (± 30 min) after M3814.
Premedication Avelumab		X				X	X	Required only for first 4 avelumab infusions, as needed thereafter. See Section 6.5.5.
Avelumab		x				x	x	800 mg iv Q2W until PD; on Day 1 avelumab will be given prior to M3814. For post-PD treatment, see Section 6.6.6. For post-CR treatment, see Section 4.1.1.2.
Hematology and Serum Chemistry	x	х	X (D5)		х		X Q4W Starting Visit 13	Baseline complete hematology and core serum chemistry analyses could be performed within Screening period (can be up to 35 days prior to the first administration of study interventions). Prior to the administration of study interventions, the most recent complete hematology and core serum chemistry results must be available and reviewed. See Appendix 6.
Dipstick Urinalysis	x	x					X Q6W Starting Visit 13	Full urinalysis (dipstick + microscopic analysis) should be performed only at Screening (can be up to 35 days prior to the first administration of study interventions). If dipstick urinalysis at other assessments is abnormal, full analysis should be performed. See Appendix 6.
Free T4, TSH	x	X Q6W Starting Visit 2						
12-Lead resting ECG	x	X					х	The assessment should be performed after the participant has been in supine position breathing quietly for ≥ 5 min.
Tumor Assessment (RECIST v 1.1)	х							Tumor imaging by CT or MRI at Baseline to document tumor lesion burden. Can be up to 35 days prior to treatment start.

Study Period	Screeni ng	DLT Evaluation Period Week 1 to 4 (M3814 + RT + avelumab)					4	Notes
Study Visit	1	2	3-6	7-10	11	12	13	
Study Day (± Visit window)	-35 to -1	1	2-5 (± 1)	8-11 (± 1)	12	15 (± 1)	29 (± 1)	
M3814		x	x	x	x			M3814 QD 5 d/wk (only on days of radiation). See Section 6.6.5.2.
RT 3 Gy × 10 (5 FD/W)		x	x	X	х			RT 3 Gy/fraction, 5 FD/wk. RT to be given 1.5 h (± 30 min) after M3814.

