4.1.1.2 Treatment Period

The treatment period will begin at the first dose of M3814 which will be administered continuously in combination with avelumab for Part A and Part FE, and with avelumab and RT for Part B.

Part A and Part FE: M3814 will be administered BID continuously, in combination with avelumab Q2W starting on Day 1 until PD or unacceptable toxicity.

Part B: M3814 will be administered QD. Radiotherapy will be given at the dose of 3 Gy per day. M3814 and RT will both be given starting Day 1 for 5 days/week for 2 weeks. Avelumab will be administered Q2W starting on Day 1 until PD or unacceptable toxicity.

Part A and Part B:

Dose-limiting toxicity (DLT) Assessment Period: will last 3 weeks in Part A and 4 weeks in
Part B (after the first administration of study intervention) for the evaluation of acute systemic
and local toxicity in all participants. The DLT assessment period in Part B will be longer than
for Part A because toxicities related to radiation including Radiation-Induced Lung Toxicities
(RILT) might occur within a few weeks to months after radiation. Therefore, additional RT
Safety Follow-ups are scheduled at 1, 3, and 12 months after the end of RT to investigate these
potential late toxicities.

Part FE:

 FE Assessment Period: will last 3 weeks (after the first administration of study intervention) for the evaluation of the effect of food conditions (fasted/fed) on M3814 PK.

Part A, Part B, and Part FE:

Participants who have experienced a confirmed complete response (CR) should be treated for a
minimum of 12 months with avelumab + M3814 in Part A and Part FE or avelumab in Part B
based on clinical judgment of benefit and/or until disease progression, unacceptable toxicity,
after confirmation of response as specified in the protocol. Where a participant with a confirmed
CR relapses after stopping treatment, during Long-term Follow-up, but prior to the
End-of-Trial, 1 reinitiation of treatment is allowed at the discretion of the Investigator and

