8.2.3 Electrocardiograms

12-lead ECG will be obtained as outlined in the Schedule of Activities using an ECG machine that automatically calculates the heart rate and measures PR, QRS, QT, and Fridericia's Correction Formula (QTcF) intervals. Refer to Section 7 for QTcF withdrawal criteria and any additional QTcF readings that may be necessary. 12-lead ECGs will be in triplicate in Part A and Part FE but not Part B.

For Part A and Part FE, at each time point at which triplicate ECG are required, 3 individual ECG tracings should be obtained as closely as possible in succession, but no more than 2 minutes apart. The full set of triplicates should be completed in less than 4 minutes.

Electrocardiograms will be recorded after the participant has been in a supine position breathing quietly for at least 5 minutes.

In Part A and Part FE: Assessments should be performed predose and 1, 2, and 6 hours postdose before blood collection for PK, Pd, and pharmacogenomic sampling, with a triplicate 12-lead ECG being performed first, followed by vital signs after the morning dose only. The schedule times may be modified based on emergent PK data.

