#### Definition of baseline

In general, the last non-missing measurement prior to the first study intervention will serve as the baseline measurement. Study intervention includes avelumab, M3814, and in the case of participants in Part B, RT. If the time of an assessment and/or the time of the initial dosing are unknown and dosing date and assessment date are the same, the following rule is used: assessments intended to be completed prior to dosing, as per protocol, and completed on scheduled visits are assumed to have been performed prior to dosing and may be selected as baseline; assessments completed on unscheduled visits are assumed to have been performed after dosing and are not eligible for selection as baseline. Unscheduled assessments which occur unambiguously prior to the start of any study intervention are eligible for selection as baseline.

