~	1		1	Baseline*
1	4	1	101	Visit 1 Day 1*
5	18	15	102	Visit 2 Day 15*
19	25	22	103	Visit 3 Day 22*
26	32	29	104	Visit 4 Day 29
33	46	43	105	Visit 5 Day 43
47	60	57	106	Visit 6 Day 57
61	74	71	107	Visit 7 Day 71
75	88	85	108	Visit 8 Day 85
* Visit also includes ECG assessment.  Further vital sign assessments are scheduled at each biweekly visit, and the following algorithm can be applied:				
Y-10	Y+3	Y = (X-2) * 14 + 1	100+X	Visit X Day Y

Table 4: Visit Window Definition for Lab Assessments for Part B Participants

Assigned Study Day (Inclusive)		Planned Study	Analysis Visit	
From (AWLO)	To (AWHI)	Day (AWTARGET)	(N) (AVISITN)	Analysis Visit (AVISIT)
-35	-1	-1	100	Screening
~	1		1	Baseline
1	1	1	202	Part B Visit 2 Day 1
2	7	5	206	Part B Visit 6 Day 5
8	15	12	211	Part B Visit 11 Day 12
16	43	29	213	Part B Visit 13 Day 29

Table 5: Visit Window Definition for Vital Sign & ECG Assessments for Part B Participants

Assigned Study Day (Inclusive)		Blanned Study	Analysis Visit	
From (AWLO)	To (AWHI)	Planned Study Day (AWTARGET)	Analysis Visit (N) (AVISITN)	Analysis Visit (AVISIT)
-35	-1	-1	200	Screening
~	1		1	Baseline
1	1	1	202	Part B Visit 2 Day 1*
2	2	2	203	Part B Visit 3 Day 2
3	3	3	204	Part B Visit 4 Day 3
4	4	4	205	Part B Visit 5 Day 4
5	5	5	206	Part B Visit 6 Day 5
8	8	8	207	Part B Visit 7 Day 8
9	9	9	208	Part B Visit 8 Day 9
10	10	10	209	Part B Visit 9 Day 10
11	11	11	210	Part B Visit 10 Day 11
12	13	12	211	Part B Visit 11 Day 12
14	16	15	212	Part B Visit 12 Day 15
17	30	29	213	Part B Visit 13 Day 29*
* Visit also includes ECG assessment.				

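### Part B schedules no ECG timed to M3814 exposure, so its ECG endpoint cannot reliably show or attribute an acute M3814 effect

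*Protocol*

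**What the plan says.** **Dosing.** Protocol Section 4.1.1.2 states for Part B: "M3814 and RT will both be given starting Day 1 for 5 days/week for 2 weeks". Table 2 of Section 1.3 marks M3814 at Visits 2 to 11 only, nominally Days 1–5 and 8–12, and on Day 1 places avelumab before M3814.

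**ECGs in Part B.** The Table 2 row has marks at Screening, Day 1 and Day 29. Days 2–5, 8–12 and 15 are blank. The note reads "The assessment should be performed after the participant has been in supine position breathing quietly for ≥ 5 min" and gives no pre- or postdose time. Table 3 adds one ECG, at EoT. SAP 9.2.3, Table 5, agrees: only "Part B Visit 2 Day 1" and "Part B Visit 13 Day 29" carry the ECG asterisk.

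**ECGs in Parts A and FE.** Section 8.2.3 requires triplicates there and not in Part B, and sets times: "In Part A and Part FE: Assessments should be performed predose and 1, 2, and 6 hours postdose before blood collection".

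**Endpoint and analysis.** The Part B secondary safety endpoints include "clinically significant abnormal ECG, marked changes in ECOG PS". SAP 15.5.1 tabulates heart-rate, QRS and QTcF abnormalities over the on-treatment period. SAP 9.1 ends that period at the earliest of 30 days after the last study intervention, the day before a new anticancer drug, or death. For baseline it says that "the last non-missing measurement prior to the first study intervention will serve as the baseline measurement".

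**The concern.** An ECG endpoint for a combination that contains a short course of M3814 should include at least one planned reading while M3814 is on board. Part B guarantees none. The only scheduled tracing that could be one is Day 1, and its place relative to the dose is left open.

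Two things follow.

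- The SAP table will call the Day 29 tracing on-treatment, although M3814 stopped weeks earlier. A reader of a clean Part B table cannot see this.
- The same Day 1 tracing is a baseline at one site and an on-treatment value at another, depending on local habit. The SAP rule for unknown times does not settle it. That rule relies on what the protocol intended to be done before dosing, and the protocol states no such intent for this ECG. By contrast, Table 2 says explicitly that the Day 1 physical examination comes before the start of study intervention.

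The protocol treats QTc as relevant: exclusion criterion 2 covers a history of long QTc syndrome with QTcF above 480 ms. Part B also allows thoracic targets and sets heart dose constraints (Appendix 8, Table 23).

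**Working it through.** The plan states no figure to reproduce. The check is day arithmetic on the schedule.

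**1. Gap from the last M3814 dose to the Day 29 ECG.** Inputs: 10 doses on working days; any start weekday (Appendix 8); visit window ±1 day (Table 2); RT delay of up to 7 days in total (Table 15, footnote c). Gap = ECG day − last M3814 day.

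| Start | Last M3814 day | Gap to Day 29 | With ±1 day | Shortest, with 7-day delay |
|---|---|---|---|---|
| Monday | 12 | 29 − 12 = 17 | 16–18 | 28 − 19 = 9 |
| Tuesday to Friday | 14 | 29 − 14 = 15 | 14–16 | 28 − 21 = 7 |

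**2. Drug left at that time.** The documents give no M3814 half-life. I assume a range of 6 to 24 h; fraction remaining = 0.5^(hours ÷ half-life).

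- 24 h: 0.5^17 = 0.0008% at 17 days; 0.5^7 = 0.8% at 7 days.
- 12 h: 0.5^14 = 0.006% at 7 days.
- 6 h: 0.5^28, effectively zero, at 7 days.

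**3. How Day 29 is classed.** Even counting only M3814 and RT, the on-treatment period would run to Day 12 + 30 = Day 42, and continuing avelumab extends it. Unless a new anticancer drug has started, Day 29 counts as on-treatment.

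**4. How Day 1 is classed under SAP 9.1.**

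- Before any dosing: it is the baseline. Scheduled treatment-period ECGs on M3814: 0.
- After avelumab but before M3814 (possible given the Day 1 order): it is on-treatment, but not on M3814. Count: 0.
- After M3814: it is on-treatment and on M3814, with Screening as baseline. Count: 1, at an unspecified time.

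Part B therefore plans at most one single tracing on M3814 days. Part A plans 3 days (1, 15, 22) × 4 times × 3 replicates = 36 tracings, of which 3 × 3 × 3 = 27 are postdose.

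**5. Existing postdose contacts.** Part B participants take M3814 on site (Section 6.4). Table 6 already draws M3814 PK at 1, 2, 4 and 6 h on Day 1.

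**The case against.** The strongest reply is that the lighter Part B schedule is deliberate. Section 8.2.3 says so, and the M3814 ECG question is assigned to Parts A and FE. Example single doses in Part A run from 50 to 800 mg, against 50 to 300 mg in Part B. Some M3814 background is redacted, so a rationale may exist that cannot be seen. This stands as a reason for moderate weight. It does not close the gap: Part A has no RT, its dose levels are examples and escalation may stop early, and omitting triplicates does not explain omitting a time.

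Second, the endpoint belongs to the triplet and is not a QT study of M3814. That also stands. Day 29 and EoT tracings can reveal avelumab-related or lasting abnormalities. Pulse, blood pressure and adverse events are collected throughout Days 1–12, unscheduled ECGs count towards worst values, and an early EoT may fall close to a dose. None of these is a planned ECG on M3814.

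Third, one Day 1 tracing after avelumab, around an RT fraction, in cohorts of 3 to 6 would not isolate M3814. True. It would give a defined reading on exposure, which the plan now lacks.

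A reader might go further and infer that the Part B ECG data carry no information, or that they will be shown beside Part A as equivalent. The documents support neither. The first fails for the reasons in the second reply. On the other, SAP 6.2 presents each part in separate outputs, and SAP 9 rules out aggregation across parts.

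**Conclusion.** The concern holds, as a limit on what the Part B ECG endpoint can reliably show or attribute: an acute effect of M3814 given with avelumab and RT. Between the first dose and EoT the schedule has one untimed Day 1 tracing and one on Day 29. The latter is nominally 17 days after M3814, 15 days for starts other than Monday, and never fewer than 7 days if the 7-day delay limit is kept. That M3814 has largely cleared by then rests on the assumed half-life of at most 24 h. The gap in days does not depend on it.

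It would be too strong to say that the endpoint cannot show an M3814 effect at all, or that the study leaves M3814 ECG effects unexamined. The Day 1 tracing may happen to be postdose, persistent effects may be seen later, and Part A is planned to collect dose-timed ECGs.

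A separate point concerns all parts. Section 8.2.3 sends the reader to Section 7 for QTcF withdrawal criteria, and Section 7 states no explicit QTcF rule. Section 7.1 offers at most an indirect route, through the occurrence of a clinically relevant exclusion criterion. These passages must be reconciled.

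**What to change.** - **Protocol Table 2, ECG note:** state that the existing Day 1 ECG is taken at one of the existing post-M3814 PK times, for example 2, 4 or 6 h, the same for all sites. RT is due 1 to 2 h after M3814, so a later time may be easier to keep.
- **SAP 9.1 and Table 5:** name the Screening ECG as the Part B ECG baseline and mark Day 1 as post-M3814.
- **SAP 15.5.1:** state that Part B ECGs from Day 29 onward are off M3814.
- **Sections 8.2.3 and 7:** reconcile the QTcF cross-reference.

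Cost: no extra visit and no extra ECG. The baseline ECG may be up to 35 days old, and the on-exposure reading remains one unreplicated tracing.

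Moving the Day 29 ECG to a dosing day is not recommended. It would remove the only scheduled ECG between Day 1 and EoT.
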